6.0 STUDY DESIGN

6.1 Overview of Study Design

We propose to implement OUD-CDS in a large multi-site clinic randomized pragmatic trial to evaluate its impact on practice process measures and patient outcomes. We also aim to prepare for scalability by evaluating facilitators and barriers to implementation, determining the costs of implementation and maintenance, and assessing cost effectiveness of the OUD-CDS. The trial will include three large geographically dispersed care systems that constitute a racially, ethnically and socioeconomically diverse patient population. At least 30 clinics will be randomized to receive the OUD-CDS intervention or UC. Randomization will be stratified by care system, with key pre-randomization clinic measures balanced across treatment arms. Randomization in each healthcare system will be approximately 1:1. In intervention clinics, the OUD-CDS will identify patients who are at high risk for or previously diagnosed with OUD; use data stored in the EHR for these patients to assemble treatment recommendations tailored to the current needs of each patient; display these recommendations via the OUD-CDS user interface; and store analytic data from all targeted visits. In UC clinics, the OUD-CDS will run invisibly in the background to identify high-risk and OUD diagnosed patients, assemble treatment recommendations and store analytic data from all targeted visits. The targeted visits for each study-eligible patient in all randomized clinics will be the index visit, the first visit at which the OUD-CDS identifies that the patient is eligible, and all post-index visits through the end of the observation period. Patients who are identified as eligible during the accrual period and meet all inclusion and exclusion criteria will be considered for inclusion in the primary outcome analyses. Patient outcomes will be derived from the data elements stored by the OUD-CDS at all targeted visits. To the extent it is available, EHR data from the year prior to the index visit through the end of the observation period will be included in primary and secondary analyses. Process outcomes at or following the index visit (Aims 1 and 2), and clinical outcomes following the index visit through the end of the observation period (Aim 3), will be compared between patients cared for in intervention and UC clinics to assess the effectiveness of OUD-CDS.

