Definition of High Risk: Algorithms determine when a patient is identified as being at high risk for OUD or opioid overdose, and, in intervention clinics, this will trigger a best practice alert to be displayed for a particular patient at a particular clinic encounter. These algorithms, like all of the OUD-CDS algorithms, are housed on a web platform that interacts with the EHR to pull data elements to run risk equations and determine patient eligibility. We anticipate that how the algorithms will identify patients at high risk of OUD or opioid overdose will evolve over time as our ability to predict risk improves. In early phases of this study, we may use EHR data elements such as long-acting opioid prescriptions, concomitant benzodiazepine and opioid prescriptions, mental health diagnoses, alcohol and substance use diagnoses and previous opioid overdose diagnoses to identify patients at increased risk of OUD or opioid overdose.[31] We may also use, in care systems where this is available, a risk equation developed and validated by EPIC that estimates a patient's risk of OUD or opioid overdose within the next year. As the study progresses, we anticipate incorporating additional calculators for high risk into our algorithms. In work funded by NIDA (1R01DA047724-01, PI [name]), we are developing risk calculators for suicide in people with OUD, as well as risk calculators for unintentional opioid overdoses, in a population of nearly 8 million patients across 7 care systems. Variables in these risk models will include prescription opioid use, prescription opioid use reduction, prescription opioid discontinuation, opioid-related overdose, OUD and/or MOUD prescription, and illicit opioid use.

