As more sophisticated risk equations for OUD and opioid overdose risk become available, our team will write new draft algorithms to identify patients at risk in Visio. Once we have a good understanding of how these draft algorithms would work with the data available to us in EPIC, we will meet with the DSMB to discuss this potential change in identification of at-risk patients to present our proposed changes, receive feedback, make any necessary edits and request approval. Once approved, these risk equations would replace the previous risk equations in our algorithms at a pre-specified and documented date and time, and would be used to identify patients at risk of OUD or opioid overdose. Any and all changes in these OUD-CDS algorithms will be documented in a log to allow us to take these changes into account in analyses and understand how such changes may have influenced study outcomes. For each patient at each encounter, we will know why that patient was identified as high risk.

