11.2 Mixed Methods

We will rely on the RE-AIM framework to construct a quantitative monitoring system that will identify implementation problems as early as possible, followed by selective interviews and surveys to identify specific barriers and facilitators that can be addressed iteratively as each site initiates the OUD-CDS. We will also document any adaptations made and their impact on our measures. The RE-AIM constructs and measures are listed in **Table 2**.

Table 2. RE-AIM Evaluation and Monitoring System

Constructs	Evaluation Goal	Quantitative Measures
Reach	Maximize the eligible patients receiving the OUD-CDS during primary care encounter	% of eligible encounters in intervention clinics for which the OUD-CDS is opened and used
Effectiveness	Maximize the effectiveness of the OUD-CDS tool to achieve study outcomes.	% of study eligible patients who receive an OUD diagnosis, naloxone, MOUD, referral for OUD treatment, or screening for infectious diseases or mental health conditions
Adoption	Minimize the variation in Reach, Effectiveness, and Implementation across different clinics and clinicians	Size of one standard deviation among clinics and among clinicians in the process and outcome measures listed under reach and effectiveness
Implementation	Maximize fidelity to optimal intervention with patients or modify the intervention to fit clinic realities	% of patients with an OUD diagnoses who refill MOUDs, attend therapy appointments or return for follow-up care
Maintenance	Maintain the optimal level of patient intervention over time	Change in RE-AIM measures over time

The following methods will be used to conduct an assessment of the reasons for problems identified by the monitoring system and identification of barriers and facilitators to the use of the OUD-CDS through a mixed-methods approach guided by the measures in the monitoring system

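### Maintenance in Table 2 is a raw trend with no usual-care comparator, so changes in who is indexed, in the algorithm or in outside conditions can pass for loss or gain of effect, or hide real decay

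*Combined protocol and SAP*

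**What the plan says.** Section 11.2 sets up a RE-AIM evaluation and monitoring table. Its Maintenance row is measured as "Change in RE-AIM measures over time". Two of the rows it follows matter here:

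- Effectiveness is the percentage "of study eligible patients who receive an OUD diagnosis, naloxone, MOUD, referral for OUD treatment" (or comorbidity screening). No comparator is named, and the wording does not restrict it to one arm.
- Reach is the percentage "of eligible encounters in intervention clinics for which the OUD-CDS is opened and used".

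The same section promises: "We will also document any adaptations made and their impact on our measures". No comparator is named there either.

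Three other parts of the plan bear on how such a trend reads:

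- The index date is the first visit at which the tool finds the patient eligible (Section 11.1), and accrual lasts 7 to 18 months by system (Section 7.2).
- Section 8.3 states: "We anticipate that how the algorithms will identify patients at high risk of OUD or opioid overdose will evolve over time". After discussion with and approval by the DSMB, "these risk equations would replace the previous risk equations in our algorithms at a pre-specified and documented date and time". Changes "will be documented in a log to allow us to take these changes into account in analyses", and the reason each patient was flagged is stored.
- Section 6.1 states: "In UC clinics, the OUD-CDS will run invisibly in the background to identify high-risk and OUD diagnosed patients". Section 6.2 confirms that identification works the same way in both arms over the same period.

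**The concern.** A before-after trend in the Effectiveness percentage mixes at least four things: the effect of the tool, the case mix of patients being indexed, the algorithm version, and outside conditions. Patients already eligible at go-live who attend often will tend to be indexed first and infrequent attenders later. A new risk equation changes who is flagged. Waiver incentives may be offered in both arms (Section 10.7), and the implementation log itself anticipates changes in opioid policy and guidelines (Section 11.2, part D). Each of these can move the percentage in UC clinics as well.

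No other section tests whether the effect persists through the intervention period. The time points in Section 13.4 are 0, 30 and 90 days after index. The treatment-by-time terms in Sections 13.3 and 13.9 compare before and after index. The modifiers in Section 13.6 do not include time since go-live. What is at stake is the Aim 5 account of whether the tool kept working and which adaptations helped, because Sections 11.2 and 13.3 carry the monitoring data into the dissemination conclusions.

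**Working it through.** **Plan's own figure.** The documents attach no number to Maintenance. As an anchor, take the H1.1 power example in Section 13.2.2.1 (30 clinics of 50 patients, ICC 0.03, 5% versus 11.35%). The design effect is 1 + 49 × 0.03 = 2.47, and the effective number per arm is 750 / 2.47 = 303.6. Power is then 0.816 by the normal approximation, against the stated 0.80. The odds ratio is (0.1135/0.8865) / (0.05/0.95) = 2.43, as stated.

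**Check 1: change of mix, constant odds ratio 2.43.** Take two strata with UC rates of 10% and 2%, both within the Table 3 range. Odds of 0.1111 × 2.43 give an intervention rate of 21.26%. Odds of 0.02041 × 2.43 give 4.725%. Assume the high-rate stratum falls from 60% to 30% of those indexed (the documents give no shares).

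| | Early | Late |
|---|---|---|
| Intervention | 0.6 × 21.26 + 0.4 × 4.725 = 14.65% | 0.3 × 21.26 + 0.7 × 4.725 = 9.69% |
| UC | 0.6 × 10 + 0.4 × 2 = 6.80% | 0.3 × 10 + 0.7 × 2 = 4.40% |
| Odds ratio | 2.35 | 2.33 |
| Risk difference | 7.85 points | 5.29 points |

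The raw figure drops 4.96 points with no change in effect. If the mix moves the other way, it rises from 9.69% to 14.65%. The odds ratio is almost flat. The risk difference is not, so the scale of the contrast matters.

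**Check 2: order of indexing.** This is a simulation of 4,000,000 patients. All inputs are assumptions: visit rates are gamma with mean 4 per year and CV 0.8; time to first visit is exponential; everyone is eligible at go-live; log-odds of the outcome = −2.6 + 0.5 × ln(rate/4), plus ln 2 in the intervention arm.

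| Indexed in months | Share of those indexed by month 18 | Intervention | UC | Odds ratio |
|---|---|---|---|---|
| 0-3 | 59% | 13.8% | 7.5% | 1.99 |
| 3-7 | 24% | 11.3% | 6.0% | 1.99 |
| 12-18 | 6% | 8.2% | 4.3% | 1.99 |

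The relative fall from months 0-3 is 18% by months 3-7 and 41% by months 12-18. Section 7.2 plans 18 months of accrual at HealthPartners, 10 at Geisinger and 7 at Essentia, so only HealthPartners covers months 12-18.

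**Sensitivity (months 0-3 to 12-18).**

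- Slope 0.3: fall of 27%. Slope 0.8: fall of 57%. Slope 0: no drift.
- Slope −0.5: the intervention percentage rises from 13.1% to 21.2%.
- Slope 0.5 with 30% or 50% of patients becoming eligible evenly over the 18 months: fall of about 19% or 14%.
- The odds ratio against UC lies between 1.96 and 2.00 in every case.

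**The case against.** The strongest reply is that Maintenance is meant to track the level of care delivered, not the persistence of a treatment effect. Table 2 serves rapid problem-finding, with interviews to explain what it shows. For that use a raw percentage is suitable, and this stands. It does not cover the promise to document the impact of adaptations, which is a causal statement, or the later use of the monitoring data for dissemination.

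Second, Table 2 does not exclude UC clinics: eligible patients exist in both arms. That is also correct. But silence is not a contrast, and a trend pooled over arms would be no more interpretable.

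Third, algorithm changes are logged, the reason for flagging is stored, and a separate log records adaptations and policy events. These records make adjustment possible. They give no method, and they do not capture how often a patient attends. Section 13.3 leaves detail to a Statistical Analysis Plan, but describes that detail as concerning the primary outcome analyses.

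A reader might infer that the plan guarantees an apparent loss of effect. The documents do not support this. Replacement of the risk equations is anticipated and needs DSMB approval, so it is not a fixed shift. Nor does any section say that later-indexed patients have lower outcome rates. The reverse is plausible, for instance for H1.1, which counts only undiagnosed patients: frequent attenders may already have been assessed. A reader might also take the 41% fall as typical. It is the extreme of one assumed model and concerns a small late group in one system.

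**Conclusion.** The point holds for the Effectiveness measures. As written, the Maintenance trend and the before-after reading of adaptations cannot separate the tool's effect from case mix, algorithm version or outside events, although concurrent UC data exist to do so. Under the assumptions shown, the spurious relative change ranges from none to more than half, in either direction. The more typical figures are about 14% to 19%: early versus months 3-7, or with new eligibility during accrual. These sizes rest on assumed visit rates, slopes and strata and are not forecasts. The randomized tests of H1.1 to H3.2 do not use this measure and are untouched. Reach has no UC counterpart, so the criticism does not carry over to it in this form.

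**What to change.** Keep the raw percentages for monthly monitoring. For the final report, state in Table 2 that Maintenance of the Effectiveness measures, and the impact of adaptations, will be judged by the intervention-versus-UC contrast by index period since go-live:

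- Add an exploratory treatment by time-since-go-live-at-index term to the planned H1.1, H1.2, H2.1 and H2.2 models. Use each model's own scale: the odds ratio for the binary outcomes, because the risk difference still moves with case mix.
- Include as covariates care system, algorithm version or reason for identification, and prior OUD diagnosis where it applies (not H1.1).
- Judge an adaptation against UC clinics of the same system over the same months.
- Keep Reach as a trend within intervention clinics, shown separately for first eligible and repeat visits.

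No new data are needed. The cost is a wording change and one model term. The trend estimate will be imprecise, since Section 13.2.2.1 already notes that site-specific analyses detect only large effects. Algorithm version may be partly collinear with time within a system. The contrast covers only each system's 7 to 18 accrual months (up to 3 more if accrual is extended). It should therefore be reported as exploratory, with confidence intervals.

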11.3 General Measures

11.3.1 Contact Information

We will keep a list of participating primary care clinics, their administrative leaders and their PCPs on a secure server at HealthPartners. This list will include the PCP name, primary care clinic name, phone number of the clinic and provider email address. We will also keep a separate list of healthcare system administrative leaders to engage in administrative interviews, including leader name, phone number and email address. We will keep a list of patients to engage in patient interviews and surveys, including patient name, primary care clinic name, patient phone number and patient mailing address.

11.3.2 Demographics Form

We will collect age, gender, race/ethnicity, years of practice and medical specialty (primary care vs. internal medicine) for PCP participants. Patient-level data required to assess study objectives will be collected from the EHR by the OUD-CDS and stored in a secure analytic database. Data will be collected from the EHR via the OUD-CDS tool itself, with data stored in a secure server located behind multiple HealthPartners firewalls.

11.4 Measures of Primary and Secondary Outcomes

Primary and secondary outcomes will be assessed using the data collected from the EHR via the OUD-CDS, from EHR (Clarity) data pulls, through PCP surveys and qualitative interviews, patient surveys and qualitative interviews, healthcare administrator interviews, and site implementation staff interviews. The specific outcome measures are described in **Section 7.0**.

11.5 Clinical and Safety Assessments

This intervention is being delivered by way of CDS prompts to influence provider actions to incorporate evidence-based best practice standards related to OUD. Prior to implementation, we will train all intervention PCPs and their rooming staff on the importance of helping us identify any clinician-identified safety events or near-misses that may be related to the EHR or CDS. We will systematically educate them in identification of potential safety events and near-misses and informing us of these events via use of the Feedback Tab in the CDS or email. We will also ask PCPs to notify us of any clinical situations where their clinical judgment differs from the CDS.

Use of the Feedback Tab will automatically generate an email that is sent to study team members, including PIs and programmers. The study team will then discuss this feedback and any necessary actions, and reply to the PCP to answer the question, discuss steps taken to address the issue, or gather additional information if needed to further trouble-shoot. PCPs will be asked to submit feedback any time their clinical judgment is inconsistent with the CDS tool. Additionally, the emails of study investigators will be listed on the CDS interface for providers, and PCPs will be encouraged to contact us directly with any questions or concerns if they'd rather not use the Feedback Tab in the OUD-CDS. This feedback will be provided to the DSMB twice per year or at the frequency determined by the DSMB.

12.0 TRAINING REQUIREMENTS

12.1 Overall

A comprehensive Training Plan will be developed to incorporate general training, study-specific training, and mechanisms for competency assessment. The Investigative Team is responsible for the development of a comprehensive Training Plan, instructional material, and delivery of the training (e.g., via self-study, online, webcast, or teleconference), with the team comprised of the Lead Node, Clinical Coordinating Center (CCC), Data and Statistics Center (DSC), as well as other participating nodes and subject matter experts, as applicable. PCPs who are in primary care clinics randomized to receive the OUD-CDS will be trained on how to diagnosis and manage OUD in primary care, use of the OUD-CDS, and the importance of using the Feedback Tab to let the study team know of any issues or questions. Traditionally, we have completed such trainings at in-person lunch meetings with clinic personnel, but will also consider other training modalities, such as web-based trainings or teleconferences, depending on the standard training practices at partner sites and clinic leadership preference.

Study staff will be trained as specified in the Study Training Plan and are required to complete institutionally required training per their research site, IRB(s), and authorities with regulatory oversight. Training will include Human Subject Protection (HSP) and Good Clinical Practice (GCP), as well as protocol-specific training. Tracking of training completion for individual staff as prescribed for assigned study role(s) will be documented, endorsed by the site Principal Investigator and the Lead Node, and audited by the CCC. As changes occur in the prescribed training, the Training Plan and training documentation tracking forms will be amended to reflect these adjustments.

13.0 STATISTICAL DESIGN AND ANALYSES

13.1 General Design

13.1.1 Study Hypotheses

H1.1: Patients previously undiagnosed with OUD but identified as high risk by the OUD-CDS at an index visit will be more likely to receive an OUD diagnosis (in the problem list or as an ICD-10 visit code) in intervention clinics than UC clinics within 30 days post-index.

H1.2: Patients previously diagnosed with OUD or identified as high risk by the OUD-CDS at an index visit will be more likely to have naloxone rescue kits ordered in the intervention clinics than in the UC clinics within 30 days post-index.

H2.1: Patients identified as having OUD or as being at high-risk for OUD by the OUD-CDS at an index visit will be more likely to have MOUD orders or referral for OUD treatment within 30 days post-index in intervention clinics than in UC clinics.

H2.2: Patients identified as having OUD or as being at high-risk for OUD by the OUD-CDS at an index visit will have significantly more days covered by a MOUD prescription at 90 days post-index in intervention clinics than in UC clinics.

H3.1: Patients with OUD or identified as high-risk for OUD by the OUD-CDS who are cared for in intervention clinics will have significantly fewer post-index ED visits during the observation period (i.e., the period between each patient's index date and last observation) compared to patients cared for in UC clinics.

H3.2: Patients with OUD or identified as high-risk for OUD by the OUD-CDS who are cared for in intervention clinics will have significantly fewer post-index hospitalizations during the observation period compared to patients cared for in UC clinics.

H4.1: After controlling for demographics, baseline clinical status and prior costs of care, patients with OUD or identified as high risk for OUD by the OUD-CDS will have lower healthcare costs in intervention compared to UC clinics during the observation period (i.e., savings from lower ED visits and hospitalizations will outweigh increased costs of OUD treatment and naloxone rescue kits and OUD-CDS implementation and maintenance).

13.1.2 Primary and Secondary Outcomes (Endpoints)

Primary outcome measures will include:

1. OUD diagnosis (in the problem list or as an ICD-10 visit code) within 30 days of index visit for patients identified by the OUD-CDS as being at high risk of OU
2. Naloxone prescription within 30 days of index visit for patients with OUD or identified by the OUD-CDS as being at high risk for OUD
3. MOUD orders or referral to OUD treatment within 30 days of index visit for patients with OUD or identified by the OUD-CDS as being at high risk for OUD
4. Total days covered by an MOUD prescription in the 90 days after index visit for patients with OUD or identified by the OUD-CDS as being at high risk for OUD

Secondary outcome measures will include:

1. OUD diagnosis (in the problem list or as an ICD-10 visit code) at index or within 90 days of index visit for patients identified by the OUD-CDS as being at high risk of OUD
2. Naloxone prescription at index or within 90 days of index visit for patients with OUD or identified by the OUD-CDS as being at high risk for OUD
3. MOUD orders or referral to OUD treatment at index or within 90 days of index visit for patients with OUD or identified by the OUD-CDS as being at high risk for OUD
4. Number of ED visits during the observation period for patients with OUD or identified by the OUD-CDS as being at high risk for OUD
5. Number of hospitalizations during the observation period for patients with OUD or identified by the OUD-CDS as being at high risk for OUD
6. Healthcare costs during the observation period for patients with OUD or identified by the OUD-CDS as being at high risk for OUD, compared with healthcare costs over the same interval preceding the observation period
7. Cost of OUD-CDS implementation and maintenance
8. All-cause mortality rates during the observation period for patients at high risk of OUD
9. Fatal and non-fatal opioid overdoses during the observation period for patients at high risk of OUD
10. Rates of OUD-CDS use in intervention clinics
11. PCP ratings of confidence in treating patients with OUD prior to go-live date and 9-months following go-live date
12. Intervention clinic PCP ratings of satisfaction and acceptability of the OUD-CDS at 9 months following go-live date

Exploratory outcome measures may include:

1. Number of non-waivered PCPs becoming buprenorphine waived during the intervention period, assessed via health system administrative data
2. Number of buprenorphine prescriptions written by waived PCPs during the intervention period
3. PCP ratings of likelihood to prescribe buprenorphine for patients with OUD should no waiver be required, measured prior to go-live dates and 9-months following go-live dates
4. Adherence to therapy during the observation period, assessed via Clarity and claims data
5. Number of patients diagnosed with OUD screened for mental health comorbidities and infectious diseases during the observation period

